8.2.2 Secondary endpoints

The Secondary endpoint will be the time to the first post randomization recurrence of a pre-syncope or syncope episode (as defined in Section 7.1 and 7.1.2.1), whichever comes first.

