3.1 Objectives

The study has the primary objective of comparing time to first syncopal recurrence between

- · active group (CLS): CLS in addition to DDD pacing mode; and
- control group (CTL): sensing only, ODO mode.

Definition. According to the 2018 ESC guidelines¹, a syncopal recurrence is defined as a transient complete loss of consciousness characterized by rapid onset, short duration, and spontaneous complete recovery.

The Secondary endpoint will be the time to the first recurrence of pre-syncope or syncope, whichever comes first, compared between the study groups during follow-up

Definition. Pre-syncope is defined as any of the various signs and symptoms which are recognized by the patients as premonitory of imminent syncope but not followed by syncope.

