3.3 Secondary hypotheses

Null: the 2-year survival rate to the combined event of pre-syncope or syncope, $\Sigma(t)$, is equal in both study groups

 H_0 : $\Sigma_{CLS}(t=2 \text{ years}) = \Sigma_{CTL}(t=2 \text{ years})$

Alternative: the 2-year survival rate to the combined event of pre-syncope or syncope is different in the two study groups.

 H_1 : $\Sigma_{CLS}(t=2 \text{ years}) \neq \Sigma_{CTL}(t=2 \text{ years})$

3 Investigation plan

The study is a prospective, multi-center, double-blinded, randomized, intention-to-treat, placebo-controlled study.

Patients will be randomized to the active group or to placebo immediately after their enrolment and before any subsequent study-related procedure.

- Active group: before post-implant hospital discharge, IPG will programmed in a dualchamber DDD pacing mode with the CLS function ON.
- Control group: before post-implant hospital discharge, pacing will be programmed in the ODO mode.

Randomization ratio will be 1:1, therefore the randomization procedure will ensure that each individual patient will have (approximately) 50% chance to be assigned to the active group or to the control.

Patient selection adheres to the class IIb indication for cardiac pacing of the guidelines of the European Society of Cardiology¹.

[figure not shown]

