7.5 Evaluation of study objectives

The BIOSync CLS study (BA103, CIP ver. 7.0) gathers primary and secondary endpoints' data through self-administered patient questionnaires. In order to ensure double-blinding in endpoint assessment, the questionnaires will be collected by external personnel of an appointed CRO. This process is descripted in detail in the Charter for patient questionnaire collection and adjudication, version 2.0, 06-Mar-2017, and summarized in the below image.

At the end of the adjudication the following derived variables will be created.

Variable name	List of values	Unit of measure	Description	
pe	0 (No); 1 (Yes)	*	Occurrence of syncope episode	
time_pe	Numeric	days	If pe=1: time to the first post	
			randomization recurrence of a	
			syncopal episode;	
			If pe=0: total follow-up time	
se	0 (No); 1 (Yes)	-	Occurrence of pre-syncope or	
			syncope episode	
time_pe	Numeric	days	If pe=1: time to the first post	
			randomization recurrence of a pre-	
			syncope or syncope episode	
			whichever comes first.;	
			If pe=0: total follow-up time	

The analysis of the primary and secondary study objectives will be performed with the following code (STATA language).

stset time_pe, failure(pe==1)

*Kaplan_meier plots generation

sts graph by(rd_display), ci risktable

*Comparison of survivors functions

sts test rd_display, logrank

*Proportional hazard Cox models for major baseline predictors

stcox rd display

estat phtest

stcox gi_age

stcox gi_gender

stcox hs syncop life

stcox hs_syncop_lastyear

stcox ecg_mean_hr

stcox tt_response

stcox tt_pause_max

stcox tt_pause_type

stcox tt_time_pre_sync

^{*}Study objectives evaluation

^{*}Primary endpoint

*Secondary endpoint

stset time_se, failure(se==1)

*Kaplan_meier plots generation
sts graph, by(rd_display) ci

*Comparison of survivors functions
sts test rd_display, logrank

*Proportional hazard Cox models for major baseline predictors
stcox rd_display
estat phtest
stcox gi_age
stcox gi_gender

stcox hs_syncop_lastyear stcox ecg_mean_hr

stcox tt_response stcox tt_pause_max

stcox hs_syncop_life

stcox tt_pause_type stcox tt_time_pre_sync

stcox tt_low_bp

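### SAP 7.5 gives the secondary endpoint's time row the primary variable's name and the primary endpoint's condition, so the variable used in the secondary code is never defined

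*SAP*

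**What the plan says.** The table in SAP 7.5 has four rows.

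1. `pe`: whether syncope occurred.
2. `time_pe`: time to first syncope if `pe`=1, total follow-up if `pe`=0.
3. `se`: described as "Occurrence of pre-syncope or" syncope episode.
4. A second row named `time_pe`. Its text describes time to first pre-syncope or syncope, "whichever comes first", but its two branches are `pe`=1 and `pe`=0. The second branch reads "If pe=0: total follow-up time".

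The SAP then prints the Stata code that will be used for both objectives. The primary line, "stset time_pe, failure(pe==1" plus closing bracket, uses two defined variables. The secondary line, "stset time_se, failure(se==1" plus closing bracket, uses `se`, which is defined, and `time_se`, which appears nowhere else in either document.

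The endpoint itself is not in doubt. Protocol 8.2.2 states: "The Secondary endpoint will be the time to the first post randomization recurrence of a pre-syncope or syncope episode". SAP 3.1 has "time to the first recurrence of pre-syncope or syncope, whichever comes first", and the alternative in SAP 3.3 is that "the 2-year survival rate to the combined event of pre-syncope or syncope is different in the two study groups".

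**The concern.** The fourth row is the only derivation rule for the event time of the only secondary endpoint, and it disagrees with the code that depends on it in both name and condition. The missing name will be noticed, because the secondary code has nothing to run on. The wrong condition may not be. If the row is renamed `time_se` and left conditioned on `pe`, the code runs without complaint. A patient with pre-syncope and no syncope (`se`=1, `pe`=0) is then a failure dated at total follow-up.

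The misdating can be long, because pre-syncope does not end participation. Follow-up ends at an assessed syncope or the 24-month visit (protocol 8.8.6), at withdrawal or early termination (8.8.5.1, 9.5.5), or at the study stop date (11.7.1). What is at stake is the composite hazard ratio, its Kaplan-Meier curves and its log-rank test.

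**Working it through.** **Table against code**

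| Item | Table | Code |
|---|---|---|
| Primary indicator | `pe` | `pe` |
| Primary time | `time_pe`, conditioned on `pe` | `time_pe` |
| Secondary indicator | `se` | `se` |
| Secondary time | `time_pe` again, conditioned on `pe` | `time_se`, undefined |

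A fault in reading the PDF is unlikely: `pe` stands three times in the fourth row (name and both branches), while the `se` row above it reads correctly.

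**One patient.** Take a first pre-syncope at month 3, no syncope, and follow-up complete at month 24. Then `se`=1 and `pe`=0. Conditioned on `se`, the event time is month 3. Conditioned on `pe`, it is month 24. The patient is a failure in both cases, dated 24 − 3 = 21 months late in the second.

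**Size if only the name is corrected.** The documents give no pre-syncope rate, so this is an illustration under assumptions.

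Inputs from the plan: 2-year syncope of 57% against 34%, exponential times, 64 per arm, 10% loss. Hazards per year:

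- control syncope: −ln(0.43)/2 = 0.422
- active syncope: −ln(0.66)/2 = 0.208
- ratio: 0.208/0.422 = 0.49, which reproduces the plan's hazard ratio

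Assumed inputs:

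- Control 2-year pre-syncope of 20%, 40% or 60%, with hazard −ln(1−p)/2 = 0.112, 0.255 or 0.458.
- First pre-syncope independent of syncope.
- Follow-up of 24 ± 1 months, ending at syncope.
- No early stopping at an interim analysis.

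For conversion, active pre-syncope hazard = control hazard + f × (0.422 − 0.208), where f is the share of prevented syncope that becomes pre-syncope. At f = 1 the total active hazard equals the total control hazard, so the true composite hazard ratio is 1.0. In the other scenarios the active pre-syncope hazard is a multiple of the control hazard. For example, at ×0.17 and p = 40%, the true ratio is (0.208 + 0.17 × 0.255)/(0.422 + 0.255) = 0.251/0.677 = 0.37.

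Simulated average composite hazard ratios (4,000 to 8,000 trials per scenario), for control pre-syncope of 20 / 40 / 60%:

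| Assumed effect of CLS | Conditioned on `se` | Renamed, still on `pe` |
|---|---|---|
| Planned syncope effect, all prevented syncope becomes pre-syncope | 1.0 / 1.0 / 1.0 | 0.77 / 0.76 / 0.73 to 0.75 |
| Planned, half converted | 0.80 / 0.84 / 0.88 | 0.68 / 0.69 / 0.71 |
| Planned, pre-syncope hazard unchanged | 0.60 / 0.68 / 0.75 | 0.56 / 0.62 / 0.66 |
| Planned, pre-syncope hazard ×0.49 | 0.490 / 0.486 / 0.485 | 0.490 / 0.495 / 0.515 |
| Planned, pre-syncope hazard ×0.17 | 0.42 / 0.37 / 0.31 | 0.44 / 0.41 / 0.39 |
| No syncope effect, pre-syncope hazard equal | 1.00 / 1.00 / 1.00 | 1.00 / 1.00 / 1.00 |
| No syncope effect, pre-syncope hazard ×2 | 1.22 / 1.39 / 1.53 | 1.13 / 1.18 / 1.18 |
| No syncope effect, pre-syncope hazard ×0.5 | 0.89 / 0.81 / 0.74 | 0.93 / 0.88 / 0.86 |

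Under full conversion about 25 / 36 / 46 of 128 patients are misdated, by 13 to 14 months on average. The log-rank test then rejects in 20.8% / 26.4% / 30.5% of trials instead of about 5%, nearly always in favour of CLS.

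Late dating flatters the arm with more pre-syncope-only patients. That is the active arm if CLS turns syncope into pre-syncope, and the control arm if CLS suppresses pre-syncope strongly enough.

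**The case against.** The strongest reply is that this is a copy-and-paste slip that misleads nobody. The endpoint is stated without ambiguity in protocol 7.1.2 and 8.2.2 and in SAP 3.1 and 3.3. The fourth row's own text describes the composite, and the code pairs `time_se` with `se`. A Stata dataset cannot hold two variables of one name, so the derivation must be settled before any analysis is run. The distortion needs someone to repair the name and leave the condition beside it untouched, and nothing in the documents says that this happened or would happen. All of this stands. It limits the severity, and it makes the figures above conditional. It does not make the row correct.

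A reader might go further and infer that the slip favours the device, since protocol section 7 expects CLS to act partly by turning syncope into pre-syncope. The documents do not support that as a general statement. Protocol 3.2 also cites a crossover study of CLS with an 83% reduction in pre-syncope recurrences. That figure concerns counts, but used as a rough guide (×0.17) it makes the error work against CLS.

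A reader might equally infer that nothing is distorted when CLS has no effect on syncope. That holds only if pre-syncope is also equal between arms. If it differs, the ratio is pulled towards 1.

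**Conclusion.** The defect is confirmed by the text alone: the secondary time variable is undefined, and the row meant to define it carries the wrong name and the wrong condition. Severity is minor. The primary variables and code agree, pass or fail rests on the primary endpoint (protocol 11.5), and the intended derivation can be recovered.

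The consequence of correcting only the name has no fixed direction. It depends on the effect of CLS on pre-syncope, which the documents do not give. In the scenarios examined it ranges from a composite hazard ratio of about 0.75 where the truth is 1.0, through almost no change, to about 0.39 where the truth is about 0.31. These figures rest on assumed pre-syncope rates, independence of the two event types and no early stopping. They show why the condition must be corrected along with the name. They are not evidence of bias in the trial.

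**What to change.** Change the fourth row of the SAP 7.5 table:

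- Name: `time_se`.
- If `se`=1: days from randomisation to first pre-syncope or syncope, whichever is earlier.
- If `se`=0: total follow-up time, censored at last patient contact as SAP 7.1 provides.

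Leave the primary `time_pe` row and both `stset` lines as they are. The cost is one table row in the SAP. Code, data collection, censoring rule and sample size do not change.

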7.6 Interim analysis

Interim analyses will be performed at t=0.4 and 0.7 of the required primary endpoint events or, equivalently, after 25 and 43 endpoint events will be collected. The final analysis will be performed after the study database has been closed out. In order to keep the overall type I error at the level of 0.05, two-sided, symmetric O'Brien-Fleming boundaries generated with the Lan-DeMets spending function approach to group-sequential testing will be assumed as early stopping rules for efficacy.

t	0.40	0.70	1.00
No. endpoint events	25	43	62
Zup	3.3569	2.4445	2.0005
Z_{low}	-3.3569	-2.4445	-2.0005
р	0.0008	0.015	0.05

7.7 Clinical Investigation Plan (CIP) deviations

All CIP deviations will be classified with details of the type of deviation and the full-list will be provided in the Clinical Investigational Report (CIR).

The number (and percentage) of patients with major and minor protocol deviations will be summarized by randomization group.

A post-hoc per-protocol analysis according to the existing data gathered could be run after the evaluation of the provided deviations.

Page 14/14

References

